# 9. Statistical Considerations

# 9.1 Statistical Hypotheses

The hypotheses for the primary efficacy endpoints are defined as:

- **H1-**  $H_{01}$ :  $\mu_{1P} \le \mu_{1V}$  versus  $H_{11}$ :  $\mu_{1P} > \mu_{1V}$  where  $\mu_{1P}$  and  $\mu_{1V}$  stand for the mean change from baseline in the placebo (P) and verum (V) group in HF frequency at week 4
- **H2-**  $H_{02}$ :  $\mu_{2P} \le \mu_{2V}$  versus  $H_{12}$ :  $\mu_{2P} > \mu_{2V}$  where  $\mu_{2P}$  and  $\mu_{2V}$  stand for the mean change from baseline in the placebo (P) and verum (V) group in HF frequency at week 12.

The hypotheses for the key secondary efficacy endpoints are defined as:

- **H3-**  $H_{03}$ :  $\mu_{3P} \le \mu_{3V}$  versus  $H_{13}$ :  $\mu_{3P} > \mu_{3V}$  where  $\mu_{3P}$  and  $\mu_{3V}$  stand for the mean change from baseline in the placebo (P) and verum (V) group in PROMIS SD SF 8b total score at week 12.
- **H4-**  $H_{04}$ :  $\mu_{4P} \le \mu_{4V}$  versus  $H_{14}$ :  $\mu_{4P} > \mu_{4V}$  where  $\mu_{4P}$  and  $\mu_{4V}$  stand for the mean change from baseline in the placebo (P) and verum (V) group in MENQOL total score at week 12.

For the confirmatory efficacy analysis, a hierarchical testing approach will be applied, involving the two primary efficacy variables and the two key secondary variables. The type I error rate will be controlled at a one-sided  $\alpha$ =0.025 level. For a positive study outcome, both tests for primary variables need to be significant. As the hierarchical testing procedure follows a fixed sequence, it stops as soon as any of these tests cannot be rejected at an alpha level of 0.025 and all further tests after failing to reject one null hypothesis in the testing sequence will be considered exploratory. This fixed sequence procedure accounts for the multiplicity created by carrying out multiple tests. Moreover, all other endpoints will be summarized descriptively and therefore no multiplicity adjustment is needed.

# 9.2 Sample Size Determination

Approximately 405 participants will be randomly assigned to study intervention in a 2:1 ratio. Of these, 270 participants will be randomly assigned to elinzanetant and the other

10 MAY 2023 Page: 60 of 97

135 participants will be randomly assigned to the placebo arm. The randomization will be stratified by women with a personal history of hormone-receptor positive breast cancer or women at high-risk for developing breast cancer (maximum of 10% of participants for high-risk developing breast cancer) and by type of treatment of pre-existing condition at baseline (at least 40% of participants on tamoxifen and at least 40% of participants on aromatase inhibitors in both population groups, i.e. breast cancer and high-risk for developing breast cancer). Assuming a drop-out rate of 10% in the first 3 months, this will result in approximately 243 evaluable participants in the elinzanetant arm and approximately 122 participants in the placebo arm who completed 12 weeks of treatment. Assuming a yearly drop-out rate of 30% in the elinzanetant arm, approximately 189 participants will be available that were treated for 1 year.

The number of participants needed for this study is based on the total number of participants needed for the safety evaluation. Following the ICH E1 guideline (EMA 1995), a total of 1,500 participants are required that were exposed to at least one dose of elinzanetant 120 mg. Of these 1,500 participants 300-600 should have been treated for at least 6 months and approximately 100 for 1 year. Based on the number of participants that are available from previous phase 1 and phase 2 studies, together with the number of participants that are planned to be enrolled in ongoing and upcoming phase 3 studies, the number of participants needed for the elinzanetant arm in this study is 270, also taking into account that participants in the placebo arm receive elinzanetant after 3 months and the drop-out rates described above.

Screen failures are defined in Section 5.4. Assuming a screen failure rate of 50% approximately 810 participants need to be enrolled to achieve the required number of 405 randomized participants. More participants might be enrolled in case the screen failure rate is higher than anticipated. Additionally, further patients may be enrolled in case of an exceptionally high drop-out rate due to a trial-continuity issue.

A formal sample size justification was performed for the primary efficacy endpoints using the one-sided two-Sample T-test (equal variance) assuming at least approximate normal distribution and taking into account the drop-out rate of 10% in the first 3 months as described above. The power with treatment differences (i.e. mean change in frequency of moderate to severe HF from baseline to Week 4 or 12), with N=243 in the elinzanetant arm and N=122 in the placebo arm and assumed standard deviations are provided in Table 9-1. The data from placebo arm in SWITCH-1 study (NCT03596762 2020) was used for assumption of standard deviation.

10 MAY 2023 Page: 61 of 97

Table 9-1: Sample size justification

Primary efficacy endpoint	Standard deviation	Treatment difference Elinzanetant vs. placebo	Power %
Mean change in	3.632	-1.00	69.67 %
frequency of moderate to		-1.50	96.01%
severe HF from baseline to Week 4		-2.00	>99.9 %
		-1.00	55.38 %
Mean change in	4.29	-1.50	88.16 %
frequency of moderate to severe HF from baseline to Week 12		-2.00	98.71 %
Mean change in PROMIS SD SF 8b total score from baseline to Week 12	1.00	-0.4	94.90 %
Mean change in MENQOL total score from baseline to Week 12	1.00	-0.4	94.90 %

nQuery Version 9.1.0.0 was used for sample size calculation.

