## 8.1.1.3 Menopause Specific Quality of Life Scale (MENQOL)

The MENQOL questionnaire is comprised of 29 items assessing the presence of menopausal symptoms and the impact of menopause on health-related quality of life over the past week (Hilditch et al. 2008). The items assess four domains of symptoms and functioning: VMS, psychosocial functioning, physical functioning, and sexual functioning. For each item, the participants indicate if they have experienced the symptom (yes/no). If they select yes, they rate how bothered they were by the symptom using a six-point verbal descriptor scale, with response options ranging from 0 'not at all bothered' to 6 'extremely bothered'.

Based on the individual responses, item scores, domain scores, and a total MENQOL score are calculated. Each score ranges from 1-8, higher scores indicate greater bother.

In this study the MENQOL will be applied electronically and responded to by the participants at home and during selected in person visits at time points indicated in the SoA.

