4.3. Secondary Endpoints Analysis

4.3.1. Key Secondary Endpoints

The key secondary efficacy endpoints in this study are:

- Mean change in PROMIS SD SF 8b total T-score from baseline to Week 12
- Mean change in MENQOL total score from baseline to Week 12

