4.3.1.2. Main Analytical Approach

The same clinical questions are posed in respect of each primary and key secondary endpoint, and hence the data handling rules selected in respect of the ICEs are the same (detailed in Section 4.2.1). The key secondary endpoints will be analyzed using a mixed model with repeated measures (MMRM) model analogous to the main analysis of primary endpoints (see Section 4.2.1). For PROMIS SD SF 8b T-scores are used. For MENQOL week 1 data will not be collected, the analysis will be adjusted accordingly.

PROMIS SD SF 8b total scores (converted as T-scores), total raw scores and MENQOL total scores will be summarized descriptively by treatment group and week using the number of non-missing observations, arithmetic mean and standard deviation, median, minimum and maximum. The absolute values at various weeks and the corresponding change from baseline per week will be summarized accordingly. The change from baseline over time will be shown using line plots for means together with 95% CIs by treatment group.

version 3.0 Page: 44 of 87

Graphical summaries with the absolute change from baseline on the x-axis and proportion of participants achieving this reduction on the y-axis, by treatment group, for week 4 and 12 will be presented for the MENQOL total score and for the PROMIS SD SF 8b total T-score.

PROMIS SD SF 8b raw scores for each item will be summarized by a frequency table with the number of observations and percentage by treatment group and week. Bar charts will also be created by treatment group and week.

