6.1.2. PROMIS SD SF 8b

The PROMIS SD SF 8b includes 8 items assessing sleep disturbance over the past 7 days (Yu et al. 2011). Items assess sleep quality, sleep depth and restoration associated with sleep, perceived difficulties with getting to sleep or staying asleep and perceptions of the adequacy of and satisfaction with sleep. Participants respond to the items on a 5-point scale (scored from 1 to 5) from "not at all", "never", "very poor" to "very much", "always" or "very good". Four of the items are scored reversely. The individual item scores for a participant will be summed to derive a total raw score. Total raw scores range from 8 to 40, with higher scores indicating greater severity of sleep disturbance. Total raw scores will be converted into T-scores for comparison with population norms (United States general population). The conversion table is provided in Table 6–1. (PROMIS Sleep Disturbance – Scoring Manual). T-scores will be used in the confirmatory analysis.

In this study the PROMIS SD SF 8b will be applied electronically and responded to by the participants at home and during selected in person visits using the handheld device once weekly during the weeks 1-4 and thereafter at weeks 8, 12, 16, 26, 36, 52 and 56 (i.e. Follow-up).

version 3.0 Page: 62 of 87

Table 6-1: Sleep Disturbance 8b - Conversion Table

Sleep Disturbance 8b						
Short Form Conversion Table						
Raw Score		SE*				
8	28.9	4.8				
9	33.1	3.7				
10	35.9	3.3				
11	38.0	3.0				
12	39.8	2.9				
13	41.4	2.8				
14	42.9	2.7				
15	44.2	2.7				
16	45.5	2.6				
17	46.7	2.6				
18	47.9	2.6				
19	49.0	2.6				
20	50.1	2.5				
21	51.2	2.5				
22	52.2	2.5				
23	53.3	2.5				
24	54.3	2.5				
25	55.3	2.5				
26	56.3	2.5				
27	57.3	2.5				
28	58.3	2.5				
29	59.4	2.5				
30	60.4	2.5				
31	61.5	2.5				
32	62.6	2.5				
33	63.7	2.6				
34	64.9	2.6				
35	66.1	2.7				
36	67.5	2.8				
37	69.0	3.0				
38	70.8	3.2				
39	73.0	3.5				
40	76.5	4.4				
scu - Ctan dand						

^{*}SE = Standard Error on T-score metric

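### Is the 94.90% power for PROMIS unsound because the sample size tables give no units, and is the Week 4 power at -2.00 overstated?

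*Protocol*

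**What the plan says.** Protocol 9.2 gives power from a "one-sided two-Sample T-test (equal variance) assuming at least approximate normal distribution", with 243 evaluable participants on elinzanetant and 122 on placebo. Protocol 9.1 sets the error rate: "The type I error rate will be controlled at a one-sided" level of 0.025.

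Table 9-1 has six hot-flash rows in flashes per day, with SD 3.632 at Week 4 and 4.29 at Week 12. Two further rows cover the key secondary endpoints. One is "Mean change in PROMIS SD SF 8b total score from baseline to Week 12", the other is the MENQOL total score, and both show SD 1.00, difference -0.4 and power 94.90%. SAP Section 5, Table 5-1, repeats the table. The only source named for any SD is in Protocol 9.2: "The data from placebo arm in SWITCH-1 study (NCT03596762 2020) was used for assumption of standard deviation".

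The SAP is specific about the PROMIS scale that is tested:

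- Section 4.3.1 names the endpoint as "Mean change in PROMIS SD SF 8b total T-score from baseline to Week 12".
- Section 4.3.1.2 says "For PROMIS SD SF 8b T-scores are used".
- Section 6.1.2 says "T-scores will be used in the confirmatory analysis".

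SAP Table 6-1 converts raw totals of 8 to 40 into T-scores of 28.9 to 76.5. MENQOL is on a much shorter scale (Protocol 8.1.1.3): "Each score ranges from 1-8, higher scores indicate greater bother".

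**The concern.** PROMIS is the third hypothesis in the fixed sequence, and MENQOL, the fourth, is confirmatory only if PROMIS succeeds. A reader would want to know what sleep effect the 94.90% refers to, and the table does not say. Its SD column sits beside hot-flash rows in natural units, and the only SD source named is an earlier trial's placebo arm. The natural first reading is therefore scale points.

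That reading does not fit the scale. If -0.4 meant T-score points, the SD of change would have to be 1.00 point, yet SAP Table 6-1 puts the standard error of a single score at 2.5 or more. At a larger SD, a literal -0.4 points would have very little power, and the stated figure would not describe the confirmatory test at all. Week 4 power at -2.00 also fails to reproduce as printed, which makes the table look careless.

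**Working it through.** **Inputs.** n1 = 243, n2 = 122 and one-sided alpha 0.025 (Protocol 9.1 and 9.2); SDs and differences from Table 9-1; T-score conversion and standard errors from SAP Table 6-1.

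**Formula.** Power of the equal-variance two-sample t-test is 1 - F(t_crit; df, ncp), where F is the noncentral t distribution function, df = 243 + 122 - 2 = 363, and ncp = difference / (SD x sqrt(1/243 + 1/122)). The square root is 0.11096.

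**Reproducing the table.**

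| Row | SD | Difference | ncp | Stated | Computed |
|---|---|---|---|---|---|
| Hot flashes, Week 4 | 3.632 | -1.00 | 2.48 | 69.67% | 69.67% |
| | 3.632 | -1.50 | 3.72 | 96.01% | 96.01% |
| | 3.632 | -2.00 | 4.96 | >99.9% | 99.86% |
| Hot flashes, Week 12 | 4.29 | -1.00 | 2.10 | 55.38% | 55.38% |
| | 4.29 | -1.50 | 3.15 | 88.16% | 88.16% |
| | 4.29 | -2.00 | 4.20 | 98.71% | 98.71% |
| PROMIS and MENQOL | 1.00 | -0.4 | 3.60 | 94.90% | 94.90% |

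Every cell matches to two decimals except Week 4 at -2.00.

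**The Week 4 cell.** The shortfall is 99.9 - 99.86 = 0.04 percentage points, and 99.86 rounds to 99.9. No alternative convention explains it. Using the randomised 270/135 gives 99.94% here but 74.08% in the first row, where the table has 69.67%. One-sided alpha 0.05 gives 99.95% here but 79.73% in the first row. It is a rounding slip with a stray inequality sign.

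**What the PROMIS row can mean.** The ncp contains only the ratio difference/SD, so 94.90% holds in any metric where that ratio is 0.4. Which metric was meant has to be inferred:

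- *T-score points.* Table 6-1 gives single-score standard errors of 2.5 to 4.8. Two independent errors of 2.5 alone give an SD of change of 2.5 x sqrt(2) = 3.54. One raw point is worth 1.0 to 4.2 T-points, so -0.4 is less than one raw step. SD 1.00 is not plausible here.
- *Summed raw points.* For raw scores 20 to 32 the step is 1.0 to 1.1 T-points and the standard error 2.5, which is about 2.3 to 2.5 raw points. SD 1.00 is not plausible here either.
- *Standardised effect.* PROMIS and MENQOL are on different scales but carry the same 1.00 and -0.4. That is what one would enter for a generic effect of 0.4 SD.

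**Size of the literal reading.** The documents give no SD of T-score change, so these SDs are assumptions. For -0.4 T-points, power would be 17.3% at SD 3.54, 10.7% at SD 5 and 5.5% at SD 10. The same 0.4 SD effect would be 1.4, 2.0 and 4.0 T-points at those SDs, with power 94.90% each time. The low figures come only from holding -0.4 fixed while changing the SD, on a reading that the conversion table already makes implausible.

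**The case for a change.** The best case for acting is that a power figure for a confirmatory endpoint should be interpretable without inference. Nothing in either document labels the row as standardised, while the column heading and the stated SD source point to natural units. The sponsor chose to print key secondary power, and the SAP carried the row over under its general name even though the tested endpoint had become the T-score. The standardised reading is also not proved. Protocol 10.7.2 speaks of the mean of the total score. If that loosely meant a per-item mean on the 1 to 5 response scale, 1.00 and -0.4 would correspond to 8 x 1.00 = 8 and 8 x 0.4 = 3.2 summed raw points, which Table 6-1 does not rule out.

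What stands is that the metric is unstated, and that the strict inequality at Week 4 is not met. What does not stand is any inference of low power for PROMIS or MENQOL: with no SD of change in the documents, none can be drawn. The per-item possibility does not disturb the 94.90% either, since the ratio is still 0.4.

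**Conclusion.** No change to the plan follows. The 94.90% is arithmetically right for an effect of 0.4 SD at 243 and 122 participants, one-sided 0.025. The row lacks a statement of its metric, and an analyst reading it beside the identical MENQOL row and SAP Table 6-1 would sensibly take both as standardised effects. That is an inference, because the documents neither say so nor give an SD of change.

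Nothing in the analysis depends on the label. The SAP fixes the T-score as the tested scale in three places. Protocol 9.2 bases the number of participants on safety exposure and describes the formal power justification as being for the primary endpoints, so the key secondary rows are supporting information. Labelling the row would leave the sample size, model, alpha, test order and every reported result as they are.

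The Week 4 figure of 99.86% against a printed value above 99.9% is a clerical slip of 0.04 percentage points, on which no decision rests.

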# 9.3 Analysis Set

For the purposes of analysis, the following analysis sets are defined in Table 9-2.

Table 9-2: Definition of the analysis sets.

Analysis Set	Description
Enrolled	All participants who sign the informed consent form.
Full Analysis Set (FAS)	All randomized participants.
Safety Analysis Set (SAF)	All participants who receive at least one dose of study intervention.

Efficacy analyses will be based on the FAS and participants will be analyzed according to the randomized intervention. Safety analyses will be performed on the SAF and participants will be analyzed according to the intervention received.

Documentation of validity findings and assignment of participants to analysis sets will be performed according to the sponsor's applicable Standard Operating Procedures.

Details on additional subsets which may be of interest will be provided in the statistical analysis plan (SAP).

HF = Hot Flash, MENQOL=Menopause Specific Quality of Life Scale, PROMIS SD SF 8b=Patient-reported Outcomes Measurement Information System Sleep Disturbance Short Form 8b

10 MAY 2023 Page: 62 of 97

# 9.4 Statistical Analyses

#### 9.4.1 General Considerations

SAP will be finalized prior to database lock and will include a more technical and detailed description of the statistical analyses described in this section. This section is a summary of the planned statistical analyses of the most important endpoints including primary and key secondary and secondary endpoints.

If not otherwise indicated, the statistical analyses will be performed using SAS; the version used will be specified in the SAP.

The endpoints/variables collected in the study will be analyzed using descriptive statistics as appropriate. Continuous variables will be analyzed using at least the following descriptive statistics: number of non-missing observations, arithmetic mean and standard deviation, median, minimum and maximum. Where appropriate 95 % confidence intervals will be provided. Discrete data will be analyzed using frequency tables. Further details will be described in the SAP.

#### **Intercurrent Events**

Important Intercurrent Events (ICEs) for this study are defined as:

- a. Temporary treatment interruption in the week 4 defined as treatment taken <80% during weeks 1-4 OR treatment taken on <5/7 days during either week 3 or 4.
  - Temporary treatment interruption in the week 12 defined as treatment taken <80% during weeks 1-12 OR treatment taken on <5/7 days during either week 11 or 12.
- b. Permanent treatment discontinuation of randomized treatment.
- c. Intake of prohibited concomitant medications having impact on efficacy.
- d. Interruption/discontinuation in intake of adjuvant endocrine therapy defined as follows:
  - For participants using Tamoxifen: reduction of at least 50% of planned daily dosage taken during weeks 3 and 4 OR weeks 11 and 12 compared to baseline
  - For participants using Aromatase inhibitor: reduction of at least 30% of planned daily dosage taken during weeks 3 and 4 OR weeks 11 and 12 compared to baseline

The impact of these ICEs on the study results and its interpretation is addressed in Table 3-2 where the primary estimand for the primary endpoint is defined.

A low impact of the COVID-19 pandemic on missing assessments of the frequency and severity of HFs is considered due to the use of eDiary. The eDiary should be completed at home and therefore, there is no need for participants to attend the clinic for the assessment of HFs related endpoints.

COVID-19 is included as a reason for occurrence of the important ICEs in the study estimand strategy (Table 3-2).

10 MAY 2023 Page: 63 of 97

The number of deaths are considered to be small and therefore the impact of death as a potential ICEs is expected to be negligible. That will be monitored throughout the trial until the blind review and if deemed necessary, the estimand will be adjusted in the SAP before the study unblinding.

The number of observed intercurrent events will be summarized by treatment group and overall, for each intercurrent event.

# 9.4.2 Primary Endpoint

The primary efficacy endpoints for this study are:

- Mean change in frequency of moderate to severe HF from baseline to Week 4 (assessed by HFDD)
- Mean change in frequency of moderate to severe HF from baseline to Week 12 (assessed by HFDD)

# 9.4.2.1 Calculations related to the frequency and severity of HF

A diary day for the calculation of the frequency and severity of HF consists of the evening entry and the morning entry of the subsequent day. A day will be considered available for the calculation of the frequency and severity of HF, if at least the evening or the morning entry (of the subsequent day) is not missing. The daily number of hot flashes per day will be calculated as the sum of the evening and morning entries (of the subsequent day). If only the evening or morning entry is available, then only this will be used for that particular day.

The baseline value of frequency and severity of moderate to severe HF will be calculated using the available data assessed via the HFDD during the 14 days prior to the baseline visits. As per inclusion criterion 8, at least 11 days will be available for the derivation of the baseline value.

#### **Baseline value of frequency of moderate to severe HF:**

The baseline value will be calculated by aggregating the available days during the 14 days prior to start of treatment to a mean daily frequency as (total number of moderate to severe HF during the 14 days prior to start of treatment) / (total number of available days with data).

#### Frequency of moderate to severe HF during treatment:

The frequency of moderate to severe HF for each week during the treatment period will be calculated using the available data during that particular week. Specifically, for Week 4 Days 22-28 will be used and for Week 12, Days 78-84 will be used (Day 1 corresponds to start of treatment). These data will be aggregated to a mean daily frequency as (total number of moderate to severe HF during that week) / (total number of available days with data during that week). In case data is not available for more than 2 days within a week, the value for that particular week will be set to missing. Further details will be specified in the SAP.

10 MAY 2023 Page: 64 of 97

